**Data and Safety Monitoring:**

This study is low risk and runs over a short time period (4 weeks). Intradialytic hypotension is a common complication of HD. Changing the timing of exercise during hemodialysis is unlikely to cause a significant increase in the number of episodes of hypotension based on the experience of our 3 centres and data on cardiac hemodynamics with exercise in HD. As such, no data safety monitoring committee has been convened.

**Sample Size Estimation:**

We consider a 20% increase in IDH rate with intradialytic exercise in the second half of HD to be clinically significant and unacceptable. A previous study of 42 HD patients who exercised in the first half of HD observed IDH rate was 130 episodes per 100 hours of HD.

Assuming a standard deviation of 50, a sample size of 75 individuals (approximately 2250 hours of HD) will give us 80% power to observe a 20% increase in IDH rate with one-sided alpha 0.05. To account for study dropout, we will recruit a total of 90 individuals in total at the 3 sites (30 from each site Winnipeg, Calgary, Edmonton).

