exercise, completed in first half of dialysis, progressed over a 6-month period. In addition to improvement in systolic blood pressure, a significant reduction ( $p < 0.05$ ) in IDH episodes was observed. Conversely, in a cross-sectional study conducted by Dungey et al, exercise that commenced 60 minutes after dialysis start significantly increased systolic blood pressure immediately post-exercise but SBP significantly decreased (106 vs. 117 mmHg;  $p < 0.001$ ) 1 hour post exercise as compared to no exercise. Many previous studies investigating the effects of intradialytic exercise have limited exercise sessions to the first half of HD due to concerns of potentiating IDH if exercise is performed in the latter half of an HD session. Anecdotally, a number of individuals in our clinical intradialytic cycling program have cycled during the last half of HD with no ill effects. The ability to safely perform intradialytic exercise in the second half of HD would allow more flexibility in exercise timing and facilitate availability of exercise equipment and staff to help with exercise by potentially avoiding exercise at the beginning of HD (often the busiest time with the most nursing tasks). Timing of exercise later in HD treatment may also decrease frequency of cramping and restless legs symptoms, which have a propensity to occur in the latter part of HD sessions.

No study has specifically compared the frequency IDH episodes when exercise is performed during second half of HD as compared to that when exercise is performed during the first half of a HD session to fully characterize the effect of timing of intradialytic exercise and its effect on IDH.

We aim to address this knowledge gap with a randomized crossover study examining the rate of IDH when individuals in a clinical intradialytic cycling program exercise during the first half of their hemodialysis session as compared with the IDH rate when exercise is performed during the second half of hemodialysis.

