**Intervention:**

To facilitate study implementation and optimize use of exercise resources and equipment, participants at each site will be randomly split into 2 groups. Group 1 will perform 2 weeks of their usual intradialytic cycling (6 sessions) during the first half of their usual HD and then perform 2 weeks of intradialytic cycling (6 sessions) during the second half of their usual HD. Group 2 will perform the intervention in reverse order to Group 1 (See Figure 1). No washout period is required as there is no biological plausibility for carry over effect. However, as participation in the cycling program is voluntary, some participants may choose not to exercise during some of their HD sessions. We will monitor these non-cycling sessions for IDH as well and will compare IDH rate in these non-exercise sessions with IDH rate during sessions when intradialytic exercise was performed.

Participants will perform their usual duration and intensity of intradialytic cycling at each HD session as per clinical intradialytic cycling protocol procedures (see below). Prescribed exercise time and intensity will remain unchanged over the course of the study.

We will attempt to keep dialysate composition, dialyzer, dialysate temperature, HD access, dialysis duration and medications unchanged over the course of the study, but will not intervene/interfere with usual clinical care. The research assistant will record any changes to dialysis prescription related to routine clinical care on a weekly basis.

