**BP Measurement:**

We will use the initial BP measurement obtained once the patient has commenced HD (i.e. patient “hooked up” and blood present in both venous and arterial lines) for the *baseline BP*. Blood pressure will be measured as per routine procedures used in the participants’ HD units (usual arm/leg, usual BP cuff). Pre and post HD BP will be collected as per usual HD Unit practice. During HD, BP will be collected more frequently than the usual HD routine (q30 min) at q15min intervals or more frequently when clinically indicated based on patient symptoms or status. This timing will be pre-programmed into HD machines to minimize work for bedside HD nurses. However, bedside HD nurses will need to record each BP measurement on the HD run sheet. Research assistant and/or clinical exercise program kinesiologist will be present at each cycling session to ensure outcome data is being collected.

**Primary Outcome:** *Difference in rate of intradialytic hypotension* between the 2 study time periods (early and late intradialytic exercise). Rate of IDH will be reported as episodes of intradialytic hypotension per 100 hours of HD. Intradialytic hypotension will be defined as the composite of >20 mmHg drop from baseline BP OR a drop in systolic BP to <90 mmHg during HD. A >20 mmHg reduction in blood pressure is justified as this magnitude of reduction from baseline BP has been associated with occurrence of HD-induced cardiac injury. In addition, a nadir BP of <90mmHg is the only definition of IDH associated with increased risk of mortality.

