**Secondary Outcomes:**

1. Difference in rate of intradialytic hypotension (episodes of hypotension per 100 hours of HD) between the 2 study time periods (early and late dialytic exercise) as defined by a >20 mmHg drop from baseline BP AND associated with symptoms (abdominal discomfort, yawning, sighing, nausea, vomiting, muscle cramps, restlessness, dizziness or fainting, and anxiety) or requiring intervention. Although this definition is proposed by KDOQI, practically it is harder to capture for research purposes. Nonetheless, we will capture as a secondary outcome to ensure no difference in rate between two groups.
2. Difference in frequency and severity of dialysis related symptoms during the weeks that incorporate intradialytic cycling in the first part of the HD sessions as compared with symptoms when intradialytic cycling is performed during the second half of HD will be measured using the symptom burden score as measured by the Dialysis Symptom Index (DSI). The DSI (Appendix 1) is a 30-item self-administered questionnaire with low administrative burden that measures the presence (yes/no) and severity (5 point Likert-scale) of common symptoms in HD patients (cramping, nausea, dizziness, fatigue, chest pain, and shortness of breath) and has been shown to be reliable and valid. Participants will complete the DSI at time of consent and then weekly at the end of the

midweek HD session (on Wed for MWF HD shifts and on Thurs for TTS HD shifts) for the duration of the study (i.e. each participant will complete the DSI a total of 5 times over the study).

3. Difference in time for recovery post-dialysis when exercise is performed during first half of dialysis as compared with time for recovery post-dialysis when exercise is performed during the latter half of HD: at each study assessment, participants will be asked to answer the question “Approximately how much time does it take to recover from a dialysis session”. Answers will be recorded in minutes. Prolonged post-HD recovery time, defined as the answer to the question “How long does it take to recover from a dialysis session” has been identified as a troubling symptom complex and important outcome unique to individuals receiving HD.

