### **Data analysis:**

Demographic and baseline clinical data will be analyzed using the appropriate descriptive statistics and presented as mean (standard deviation), median (interquartile range), and proportion for parametric, non-parametric and categorical data, respectively. Linear mixed models will be used to analyze the associations between timing of exercise (first half or second half of HD) and intradialytic hypotension while accounting for duration of exercise, UF rate and

within patient data. Mean symptom burden score will be stratified by timing of intradialytic exercise and compared using paired Student's t-test. Similar analysis will be performed for time for recovery post HD.

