**Anticipated outcome:**

We anticipate that improved cardiac output and venous return will counteract post-exercise hypotension and that the rate of intradialytic hypotension when exercise is performed in the latter half of HD will not be significantly different than that when exercise is performed in the first half of HD.

Figure 1: Study Design

3. NKF. NKF KDOQI Clinical Practice Guidelines for Cardiovascular Disease in Dialysis Patients. 2005; [http://www.kidney.org/professionals/kdoqi/guidelines\\_cvd/guide14.htm](http://www.kidney.org/professionals/kdoqi/guidelines_cvd/guide14.htm). Accessed Sept 13, 2013, 2013.

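### A 20% rise in IDH is called unacceptable, but the plan only tests against zero, so a non-significant result need not exclude that rise

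*Protocol*

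**What the plan says.** The Sample Size Estimation section of the protocol sets the limit: "We consider a 20% increase in IDH rate with intradialytic exercise in the second half of HD to be clinically significant and unacceptable". With a reference rate of 130 episodes per 100 h and an SD of 50 that is not further described, it says that 75 individuals "will give us 80% power to observe a 20% increase in IDH rate with one-sided alpha 0.05". Ninety are to be recruited to allow for dropout.

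The research question under Methods asks whether second-half cycling gives a higher rate of IDH than first-half cycling. Under Data analysis, "Linear mixed models will be used to analyze the associations between timing of exercise (first half or second half of HD) and intradialytic hypotension", with adjustment for exercise duration and UF rate.

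Three places show what the result is meant to support:
- The introduction gives the practical motive: "The ability to safely perform intradialytic exercise in the second half of HD would allow more flexibility in exercise timing".
- Anticipated outcome predicts that the second-half rate "will not be significantly different than that when exercise is performed in the first half of HD".
- Secondary Outcomes, item 1, says of symptomatic IDH: "we will capture as a secondary outcome to ensure no difference in rate between two groups".

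The protocol nowhere compares an estimate or confidence limit with the 20%.

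**The concern.** A one-sided test against zero answers the question whether the rate is higher. The use the protocol hopes to support is the reverse: that moving exercise to the second half does no unacceptable harm. For that claim the relevant hypothesis is that the increase is 20% or more, and the data must reject it. A non-significant test against zero does not reject it, because a wide interval can include both zero and 20%.

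At stake is a recommendation on exercise timing that could rest on a null result never set against the protocol's own definition of unacceptable. The direction of the test, its alpha and the role of the 20% are all fixed in the protocol, so this is not a detail that it leaves open for a later plan.

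**Working it through.** **Inputs (Sample Size Estimation).** Reference rate 130 per 100 h; unacceptable increase 20%, so 0.20 × 130 = 26 per 100 h; SD 50, type not given; n = 75; one-sided alpha 0.05 (z = 1.645); power 80% (z = 0.842). The design is a crossover, so SE = SD_diff/√75, where SD_diff is the SD of the within-patient difference. Normal approximations are used throughout. Correlations are assumptions, since the protocol gives none.

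**1. The plan's own figure.** n = (SD_diff × (1.645 + 0.842)/26)².
- SD_diff = 50: n = 22.9, so 23. Power at n = 75 is 99.8%.
- Per-period SD 50 with correlation 0, SD_diff = 50√2 = 70.7: n = 45.7, so 46. Power at n = 75 is 93.8%.
- For n = 75 to give exactly 80% power, SD_diff = 26 × √75/2.487 = 90.6. With a per-period SD of 50 this would need a correlation of 1 − 90.6²/5000 = −0.64.

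The stated 75 and 80% are not reproduced from the SD of 50 on either paired reading, so the document does not settle which variability to believe.

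**2. When is a non-significant result certain to exclude 26?** A non-significant estimate can be as large as 1.645 × SE. Its one-sided 95% upper limit can then reach 2 × 1.645 × SE. Requiring 2 × 1.645 × SD_diff/√75 < 26 gives SD_diff < 68.4. If the per-period SD is 50, this means a correlation above 1 − 68.4²/5000 = 0.06.

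This is the condition for every non-significant result. An observed difference of exactly zero excludes 26 under the weaker condition 1.645 × SE < 26, that is SD_diff < 136.9.

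**3. Size of the gap.** The result is non-significant yet leaves 26 open when the estimate lies between 26 − 1.645 × SE and 1.645 × SE. A true increase of 10% is 13 per 100 h.

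| SD_diff | SE | Largest upper limit of a null result | Probability of gap, true difference 0 | Probability of gap, true +10% | True +20% non-significant |
|---|---|---|---|---|---|
| 50 | 5.77 | 19.0 (14.6%) | 0 | 0 | 0.2% |
| 70.7 | 8.16 | 26.9 (20.7%) | 1.2% | 4.2% | 6.2% |
| 90.6 | 10.46 | 34.4 (26.5%) | 15% | 31% | 20% |

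The last column is one minus the power in step 1.

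**4. Power of a rule against the 20% limit.** Take the contrast late − 1.20 × early. With per-period SD s and correlation ρ, its SD is s√(2.44 − 2.4ρ). At a true difference of zero its mean is −0.20 × 130 = −26. Power = Φ(26/SE − 1.645).
- s = 50, ρ = 0.5: SD 55.7, SE 6.43, power 99.2%.
- s = 50, ρ = 0: SD 78.1, SE 9.02, power 89.2%.
- SD_diff 90.6: SD about 100 (ρ = 0) to 103 (ρ = 0.8), power about 73% to 70%.

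**The case against.** The strongest reply is that the protocol does not contradict itself. It asks whether the rate is higher and sizes a one-sided test for an increase. The Anticipated outcome section is a prediction and not a decision rule, and no passage says that non-significance will be taken as proof of safety. The mixed model will yield an interval that anyone can read against 20%. With an SD of 50, power to detect a 20% rise is 94% to 99.8%, so failing to see one would be informative. All of this stands, and it limits the severity. What it leaves untouched is that a limit was named, reassurance is sought, and nothing connects the two.

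Three stronger readings are tempting and not supported:
- A reader might infer that a null result excludes the 20% only if the SD is below 68.4. That figure is for the SD of the paired difference, and it marks only when exclusion is guaranteed. Above it, many null results still exclude 26; an observed zero does so up to 136.9.
- A reader might take the 15% and 31% as the expected size of the gap. They need SD_diff 90.6, which the SD of 50 does not give at any non-negative correlation. They follow only if the stated 80% power, and not the stated SD, is the true input.
- A reader might argue that missed sessions hide a larger effect, because "some participants may choose not to exercise during some of their HD sessions". Dilution is possible, but the protocol gives no skip rate and no IDH rate for such sessions, so its size cannot be established.

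**Conclusion.** The concern holds in this limited form: the protocol names an unacceptable increase, uses it only as a difference to detect against zero, and never requires a reassuring conclusion to exclude it. A non-significant result does not exclude it by itself.

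The practical size depends on an SD that the protocol does not identify. It is nil if 50 is the SD of the difference and small if 50 is the per-period SD with zero correlation, which is a severe assumption for the same patients in adjacent two-week periods. It is material only if the variability implied by the stated 80% power is the real one. Severity is minor to moderate. The figures assume 75 evaluable patients, a reference rate of 130 and no gain from covariate adjustment.

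**What to change.** Keep the primary outcome, the linear mixed model, one-sided alpha 0.05 and n = 75, and add one decision rule. Conclude that second-half exercise does not raise IDH unacceptably only if the one-sided 95% upper limit of late − 1.20 × early lies below zero, with both means taken from the model at the same covariate values. Otherwise report that a 20% increase was not excluded. The 26 per 100 h stays a planning value and is not a second rule.

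Report the late-minus-early difference and its confidence interval in every case. Give the same contrast in sessions cycled in the assigned half as a supportive sensitivity analysis, not as a second pass/fail rule, because those sessions are self-selected. Reword Anticipated outcome to match. In Secondary Outcomes, item 1, replace the aim of ensuring no difference with reporting the difference and its interval. State which SD the 50 is.

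The cost is wording only; no data or patients are added. There are three downsides:
- A null result with a wide interval can no longer be presented as showing safety.
- Power at a true difference of zero is about 99% or 89% with a per-period SD of 50 (correlation 0.5 or 0), but about 70% to 73% if SD_diff is 90.6.
- With a small SD, the rule can be met despite a statistically significant smaller rise. At SD_diff 50, on the difference scale, this covers estimates from about 9.5 (1.645 × 5.77) to 16.5 (26 − 9.5) per 100 h. That is why the difference must always be reported.

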### **Objectives:**

1. To compare the rate of IDH when intradialytic exercise is performed in the first half of the HD session as compared with that when intradialytic exercise is performed in the second half of HD.
2. To compare the prevalence of hemodialysis related symptoms when intradialytic exercise is performed in the first half of the HD session as compared with symptom prevalence when exercise is performed in the second half of HD.

3. To compare recovery time post HD when intradialytic exercise is performed in the first half of the HD session as compared with recovery time post HD when exercise is performed in the second half of HD.

**Study Design:** Multi-centre randomized crossover study comparing the rate of IDH over a 2-week period in 90 individuals on chronic HD when intradialytic cycling is performed in the first half of HD as compared with the rate of IDH when intradialytic cycling is performed in the second half of HD for 2 weeks.

**Population/Setting:** Adults with end-stage renal disease on chronic (>3 months) in-centre HD who are already participating in the Northern Alberta Renal Program (University of Alberta Hospital, Grey Nuns Hospital, Edmonton General Hospital, and St. Paul's Dialysis Unit); Southern Alberta Renal Program (Sheldon Chumir Hemodialysis Unit, South Calgary Hemodialysis Unit, Peter Lougheed Centre, North East Dialysis Centre, Northland Dialysis Centre); or the Manitoba Renal Program (Sherbrook Centre Dialysis Unit, Central Dialysis Unit and Seven Oaks Hemodialysis Unit) clinical intradialytic cycling programs are eligible to participate. Participants will act as their own comparisons.

*Inclusion criteria:* adult ( $\geq 18$  years old); receiving three times per week intermittent hemodialysis sessions; able to communicate in English; able to provide informed consent

*Exclusion criteria:* dialysis frequency not three times per week

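### The stated 80% power for 75 patients does not follow from the protocol's own inputs, which give about 93% to 99.8%, and the SD of 50 is left undefined

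*Protocol*

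**What the plan says.** Sample Size Estimation takes from an earlier study of first-half exercise that the "observed IDH rate was 130 episodes per 100 hours of HD". It fixes the effect of interest: "We consider a 20% increase in IDH rate with intradialytic exercise in the second half of HD to be clinically significant and unacceptable". The conclusion drawn is "Assuming a standard deviation of 50, a sample size of 75 individuals (approximately 2250 hours of HD) will give us 80% power", the full claim being "80% power to observe a 20% increase in IDH rate with one-sided alpha 0.05". Recruitment is set at 90 to allow for dropout.

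Three other parts of the protocol determine how this should be computed:

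- Primary Outcome sets the scale: "Rate of IDH will be reported as episodes of intradialytic hypotension per 100 hours of HD".
- Population/Setting makes the comparison within patient: "Participants will act as their own comparisons".
- Data analysis plans a model that accounts for within-patient data: "Linear mixed models will be used to analyze the associations between timing of exercise".

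The protocol does not say whether 50 is the SD of a patient's rate in one period or of the difference between a patient's two rates. It gives neither a source for the 50 nor a within-patient correlation.

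**The concern.** Every number needed to check the power claim is in the paragraph, except which SD is meant, and the claim fails under each usual meaning of that SD. A crossover of 75 patients with an effect about half the size of the SD has far more than 80% power.

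The figure matters because of the expected result. Anticipated outcome predicts that the rate with late exercise "will not be significantly different than that when exercise is performed in the first half of HD". When a non-significant result is expected, the planned power tells the reader how likely the trial was to miss the increase called unacceptable. As written, that chance is 20%; on the stated inputs it is a few percent or less. If the inputs are not the ones actually used, the chance is unknown.

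**Working it through.** **Inputs** (Sample Size Estimation unless noted)

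- Reference rate: 130 per 100 h.
- Effect: 0.20 × 130 = 26 per 100 h.
- SD: 50, read on the scale of the rate.
- One-sided alpha 0.05 (z = 1.645); target power 80% (z = 0.842).
- n = 75, each patient contributing both periods (Population/Setting).

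**Formulas**

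- SD of the within-patient difference from a per-period SD: SD_diff = 50 × √(2(1 − ρ)). If 50 is already the SD of the difference, SD_diff = 50, which is the same as ρ = 0.5.
- Power (normal form): Φ(26 × √75 / SD_diff − 1.645), where 26 × √75 = 225.2.
- n for 80% power (normal form): (1.645 + 0.842)² × SD_diff² / 26².
- The t-based figures use the non-central t distribution with 74 degrees of freedom. Allowing for a period effect (73 degrees of freedom) leaves the powers unchanged to one decimal.

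**Attempt to reproduce 80% at n = 75, paired**

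| Meaning of SD 50 | SD_diff | 225.2 / SD_diff | Power, normal | Power, t | n for 80%, normal | n for 80%, t |
|---|---|---|---|---|---|---|
| SD of the difference | 50.0 | 4.50 | 99.8% | 99.8% | 22.9 → 23 | 25 |
| Per period, ρ = 0.25 | 61.2 | 3.68 | 97.9% | 97.7% | 34.3 → 35 | 36 |
| Per period, ρ = 0 | 70.7 | 3.18 | 93.8% | 93.4% | 45.7 → 46 | 48 |

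A per-period SD of 50 with ρ above 0.5 gives more than 99.8%, so the last row is the least favourable case unless the correlation is negative.

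**Other readings**

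- Two-sided 0.05, paired t: 99.4% (SD_diff 50) and 88.2% (ρ = 0).
- Unpaired, one-sided: 47 per group needed (94 in all). With 75 in all (37 and 38) the power is 72.1%; with 75 per group it is 93.6%.
- Unpaired with all 90 recruits (45 per group): 78.9%. This contradicts both the crossover design and the statement that 75 patients give 80%.

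**What 80% at n = 75 would require.** SD_diff = 225.2 / (1.645 + 0.842) = 90.6, that is, a per-period SD of 90.6 / √2 = 64.0 at ρ = 0. With a per-period SD of 50, the implied correlation is 1 − 90.6² / (2 × 50²) = −0.64 (about −0.6 by the t calculation too). A negative correlation of that size is implausible for the same patients in adjacent two-week periods.

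**Increase detectable with 80% power at n = 75 (paired t).** It is 14.5 per 100 h (14.5 / 130 = 11%) if SD_diff is 50, and 20.5 per 100 h (16%) if ρ = 0. The protocol's figure is 26 (20%).

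**A possible slip.** An absolute rise of 20 per 100 h in place of 20% of 130, with SD 50 and ρ = 0, gives 78.3% by t (78.9% normal) at n = 75, with 79 patients needed for 80%. This is close, but it is not what the protocol states, and the text cannot show that it happened.

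**The case against.** The strongest reply is that the SD carries no unit. The effect is given as a percentage, so 50 might be a percentage too: 50% of 130 is 65 per period. With ρ = 0, power at n = 75 is then 78.3% by t (78.9% normal), near the stated 80%. On that reading the sentence is roughly right and merely unlabelled, and printing 93% or 99% would make it worse.

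This reading has three weaknesses. The text writes a percent sign for the increase and none for the SD, which follows directly on a rate per 100 hours. It needs zero within-patient correlation in a design chosen because patients are their own controls; at ρ = 0.25, SD_diff is 65 × √1.5 = 79.6 and power by t is 87.6%. Even at ρ = 0 it needs 79 patients, not 75. It has the same effect-to-SD ratio as the possible slip above (26/65 = 20/50), so it is no separate confirmation.

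Some of the objection stands. The restated figures must depend on what the SD turns out to mean. The 99.8% is not a ceiling. A paired t-test simplifies the planned mixed model, which adjusts for exercise duration and ultrafiltration rate, and some sessions will have no exercise. Once the trial is done, the estimate and its confidence interval will say more than the planned power about what has been excluded. On the inputs as written the error is also conservative. These points limit the consequence but do not make the stated 80% correct.

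**Conclusion.** The concern holds. With an increase of 26 per 100 h, an SD of 50 on the same scale, one-sided alpha 0.05 and 75 crossover patients, power is 93.4% at zero within-patient correlation and 99.8% if 50 is the SD of the difference. The chance of missing the increase called unacceptable is therefore 6.6% down to 0.2%, not 20%. No standard paired or unpaired reading of the stated inputs gives 80% at 75.

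The result assumes that 50 is in episodes per 100 hours, that the correlation is not negative, and that a paired comparison of period rates stands in adequately for the planned model. Which of the SD, the effect size or the formula is at fault cannot be determined from the protocol. If the inputs are right, the trial has more power than claimed and the design is sound. If one is mis-stated, its power against a 20% increase is unknown. The paragraph should be corrected; nothing here argues for a larger trial.

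**What to change.** Keep the recruitment target of 90 and revise the Sample Size Estimation paragraph as follows:

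- State what the SD of 50 refers to (within-patient difference or single-period rate), its unit and its source. If it is per period, give the assumed within-patient correlation.
- Restate the power for 75 completers on that definition: about 93% if the SD is per period with zero correlation, above 99% if it is the SD of the difference. Give the increase detectable with 80% power, about 14 to 20 per 100 h (11% to 16%).
- If the SD, effect size or formula was mis-stated, correct it from its source and recompute. Do not choose a value because it returns 75.
- As a clarification only, give the assumed session length and say whether the 2250 hours cover one period or both. 2250 / 75 = 30 hours per patient, which is 5 hours per session over 6 sessions or 2.5 hours over 12.

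The cost is rewording one paragraph. Enrolment, conduct and analysis do not change.
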